Over the course of the enrollment period, we will assess each subject for 3 seven-day periods (at randomization, 3 months and 6 months post-intervention) to assure that each subject is examined in different seasons; and to evaluate the immediate as well as longer term effects of the interventions on air quality and COPD health. This approach is based on the measurement approach that we have previously demonstrated for PM reduction trials. Indoor air quality monitoring will be conducted over a 7-day period in the room where the participant is expected to spend the most time over the monitoring period.

During each home visit:

- 1) Monitors for air samples will be set up in the bedroom and in the room in which the participant spends most of his/her time.
- 2) Detailed questionnaire about home characteristics will be administered
- 3) A home inspection will be performed
- 4) Participants will be instructed on how to complete a Time Activity Diary (TAD) and symptom diary which is to be done during the time of the air monitoring period,
- 5) Outdoor air monitors will be placed in a convenient and secured location outside of each home
- 6) Dust collection in the main living area and bedroom at home.

The home visits will include the following:

- Environmental monitoring equipment set up and dust collection.
- Instructions on activity diary (TAD), symptom diary (BCSS)

Participant responsibilities:

- Activity diary (TAD daily)
- Breathlessness, Cough and Sputum Scale (BCSS daily)
- Dust collection

Household Inspection: At the time that monitoring is initiated, a trained home inspector will conduct a household inspection which will include the type, salient features and condition of the house including 1) type of home (detached, duplex, row house, apartment) and size of home; 2) type of

furnace (gas, oil, heat pump) as well as heating (radiator, forced air, electric space heater, other); 3) the presence of central or room air conditioning; dehumidifiers, or humidifiers, 4) evidence of cigarette smoke/smell of cigarettes/ashtrays. The home inspection will focus on the living/family room, the kitchen, basement, and the participant's bedroom and identify potential sources of PM, SHS and NO₂ as potential confounders to the effectiveness of home interventions.

Collect Dust samples: Study team member will vacuum settled dust samples from the room in which air pollution monitors have been placed to study allergens at home.

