03 Monthly Follow up calls (after final home visit) Individuals will also be contacted monthly for 3 months after the final home visit by study coordinators, in order to ascertain whether exacerbation events were experienced by participants. The Telephone Exacerbation questionnaire that will be administered, will take about 5 minutes.

8. Study duration and number of study visits required of research participants.

The study duration is 5 years and each subject will be enrolled for 9 months. There will be one screening assessment visit and one home air quality assessment visit (if applicable) prior to enrollment, 1 month of run-in period (including two MI sessions) and 3 home monitoring visits preceding 3 follow-up clinical visits.

9. Justification for inclusion of a placebo or non-treatment group.

Randomization: At the conclusion of the run-in period, subjects enrolled will be randomly assigned to one of two treatment arms: 1) active air cleaners and MI for SHS reduction (n=60) and 2) placement of sham air cleaners and continued smoking cessation counseling (n=60). Randomization will be stratified by season and will be performed by block to assure equal sized populations in each arm. This strategy also will ensure that each group is balanced with respect to season of randomization.

10. Treatment Groups.

- 1) **Active Treatment arm:** The active treatment arm will receive two active air cleaners with HEPA filters as well as 4 sessions of phone based motivational interviewing to support a home smoking ban and SHS reduction (in addition to the smoking cessation counseling received by all study participants).

Rationale: Two air cleaners will be deployed in the home to be consistent with our previous trials that have successfully reduced PM and improved respiratory morbidity. Air cleaners will have HEPA filters which remove PM. As portable air cleaners have not shown efficacy in reducing SHS exposure this intervention also targets a home smoking ban for both SHS and PM reduction, in order to provide greatest reduction in pollutant exposure and maximize ability to show that air quality improvement can improve health in smokers.

Active air cleaner: Air cleaners containing HEPA and capable of removing PM filter will be placed in the bedroom and room where the participant reports spending the most time. Air cleaners are

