## Analytical approach

We used descriptive statistics to characterize the patient sample, using proportions or means with standard deviations where appropriate. Descriptive statistics of central tendency and variability were generated. The distributions of each variable were assessed for normality, and appropriate transformations were made as necessary.

Primary analysis included an Intention-to-Treat analysis including all subjects randomized and having data at baseline and 6-month. The primary outcome measured included SGRQ score, and the secondary primary outcome, dyspnea, UCSD SOBQ. These outcomes were selected based on preliminary data showing an association with pollutant exposure and because they are measured with standardized instruments, which allowed for comparability across clinical trials. Furthermore, patient-reported outcomes provide insight into the practical effects of disease on everyday life and dyspnea is the primary reason for patients seeking medical care.

Secondary outcome measures included: CAT score, FEV1 and % change in FEV1 after albuterol. In addition, we evaluated respiratory exacerbations which were defined as a worsening of respiratory symptoms requiring antibiotics or oral corticosteroid use and acute health care utilization. The primary outcome for Specific Aim #2 is serum CRP concentrations, however several inflammatory and oxidative stress markers as outlined above will be measured.

In order to compare the change over time in our outcomes between treatment groups, analyses will consist of generalized linear mixed model (GLMM) to account for within-person correlations of the outcome. For the primary outcome measure we used a linear model:

$$E[Y_{ij}] = b_0 + b_1 \text{visit}_j + b_2 \text{treat}_i + b_3 \text{treat}_i * \text{visit}_j + a' \text{visit}_j * z_i$$

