where  $Y_{ij}$  is the total SGRQ score for the  $i^{\text{th}}$  individual on the visit  $j$ ,  $\text{treat}_i$  is the treatment group indicator,  $\text{visit}_j$  is a numeric visit number, and  $z_i$  is a vector of potential baseline covariates. The parameter  $b_3$  is the parameter of interest as it quantifies the effect of treatment on reducing COPD symptoms over time. For the analyses of respiratory exacerbations, we used cross-sectional logistic regression of exacerbation event (yes/no) over the course of 6-month follow-up on treatment group, adjusted by the potential baseline covariates; the parameter of interest was the odds ratio of the treatment group, as it represents the effect of treatment on the likelihood of having COPD-related exacerbations.

**Confounding:** Models above were constructed with and without adjustment for baseline covariates not adequately balanced after randomization and potential prognostic factors. Some potential covariate candidates included age, gender, race, other air pollutants (e.g., ambient pollutant concentrations), climate factors (temperature, humidity), season of recruitment, social

factors (e.g., educational attainment, household income), disease severity, medication use including inhaled corticosteroid use (participants were encouraged to bring their medications to visits), smoking pack-years, presence of HCSB, smoking status and quantity of active cigarette smoking (measured by self-report and salivary cotinine), and baseline level of the outcome.

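### The primary SGRQ equation has visit-by-covariate terms but no covariate main effects, so the adjusted treatment effect b3 depends on a visit numbering that the SAP does not give

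*SAP*

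**What the plan says.** SAP, Analytical approach, sets out "In order to compare the change over time in our outcomes between treatment groups" with a "generalized linear mixed model (GLMM) to account for within-person correlations of the outcome". No covariance structure is given. The SGRQ equation has an intercept, visit, treatment and then "b_3 \text{treat}_i * \text{visit}_j + a' \text{visit}_j * z_i". There is no term in z alone.

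The definitions below the equation say that visit "is a numeric visit number, and" go straight on to z, a vector of possible baseline covariates. They name b3 as the parameter of interest and give baseline no number. The primary set is described as follows: "Primary analysis included an Intention-to-Treat analysis including all subjects randomized and having data at baseline and 6-month".

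The Confounding paragraph says "Models above were constructed with and without adjustment for baseline covariates not adequately balanced after randomization and potential prognostic factors". Its list of candidates is open and ends with the baseline value of the outcome.

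The protocol (section 5) will "assess each subject for 3 seven-day periods (at randomization, 3 months and 6 months post-intervention". Section 8 counts a screening visit first and then "3 home monitoring visits preceding 3 follow-up clinical visits". SAP, Power, bases its calculation on b3 in the displayed model.

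**The concern.** A label such as the visit number should not affect the treatment effect. If every visit number rises by k, visit*z becomes visit*z + k*z. With no z term to absorb k*z, this is a different model with a different adjusted b3. The unadjusted b3 is not affected, because b0 and b2 absorb the shift.

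Baseline SGRQ is the sensitive case. It would be both the first response row and a covariate whose effect is forced to be proportional to the visit number. Its true relation to SGRQ is nearly constant over visits. If baseline is numbered 1, part of that constant relation is pushed into the slope, and b3 then moves with chance baseline imbalance. At stake are the error rate and power of the primary test.

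**Working it through.** **Inputs.** From SAP, Power: 60 per arm, SD 16.7, within-person correlation 0.86, residual SD 6.3, two-sided alpha 0.05, SGRQ minimal clinically important difference 4. Assumed: normal data, complete at three visits, effect accruing linearly. The 6-month effect is 2*b3.

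**The plan's own figures.** The residual SD reproduces: 16.7*sqrt(1 - 0.86) = 6.25. The 80% power for 1.75 points does not. The SE of the 6-month difference in change is 6.3*sqrt(2)*sqrt(2/60) = 1.63, and 1.75/1.63 = 1.08 gives 18.8% power. If 1.75 is read as per visit, power is 57.6%. That is a separate matter. The 4-point effect is used below so that the comparison does not rest on it.

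**Step 1: how imbalance enters b3.** Let D be the chance baseline difference in SGRQ (active minus control). With no treatment effect, the expected differences at the three visits are D, 0.86D and 0.86D. The covariate term removes a*visit*D, so the fitted 6-month effect shifts by

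shift = (0.86 - 1)D - 2aD = (-0.14 - 2a)D.

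Putting in the mean fitted a from random-intercept simulations with z = baseline SGRQ:

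- Visits 0, 1, 2: a = 0.001, shift -0.14 per point (no correction).
- Visits 1, 2, 3: a = 0.374, shift -0.89.
- Visits 2, 3, 4: a = 0.273, shift -0.69.
- Main effect of z added: a = -0.070, shift 0.00 (full correction).

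The SE of D is 16.7*sqrt(2/60) = 3.05. With visits 1, 2, 3 and the simulated shift of -0.88, an imbalance of that size moves the 6-month estimate by 0.88*3.05 = 2.7 points.

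**Step 2: simulation, z = baseline SGRQ.** 24,000 trials per effect (1,500 for random-slope fits); Wald test at 1.96; effects at 6 months.

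| Model | Type I error | Shift per point of D | Power, 4 points |
|---|---|---|---|
| As printed, 1,2,3, random intercept | 12.4% | -0.88 | 40% |
| As printed, 1,2,3, GEE, robust SE | 4.8% | -0.90 | 24% |
| As printed, 1,2,3, random intercept and slope | 5.4% | -1.29 | 15% |
| As printed, 2,3,4, random intercept | 10.5% | see step 1 | 47% |
| As printed, 0,1,2, random intercept | 5.0% | -0.14 | 69% |
| As printed, 0,1,2, GEE, robust SE | 4.9% | not computed | 69% |
| As printed, 0,1,2, random intercept and slope | 4.7% | see objection | 59% |
| Unadjusted, random intercept | 4.9% | -0.13 | 70% |
| Main effect of z added, random intercept | 4.7% | 0.01 | 72% |
| ANCOVA at 6 months | 5.2% | 0.01 | 73% |

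Monte Carlo SE is 0.2 points at 12%, 0.14 at 5% and 0.3 for power; for random-slope fits it is 0.6 at 5% and 0.9 to 1.3 for power.

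Checks:

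- First row: the model SE is 2.458 and the true SD 3.121, and 2*P(Z > 1.96*2.458/3.121) = 12.3%.
- ANCOVA SE: 16.7*sqrt((1 - 0.86^2)*2/60) = 1.56.
- Smaller separate simulations of the first row gave 11.3% to 13.6%.
- With only the baseline and 6-month visits, type I error was 4.5% with baseline 0 and 9.5% with baseline 1.

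Mean estimates were 0.0 (null) and -4.0 (effect) in every random-intercept, GEE and ANCOVA version.

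**Step 3: other covariates.** With a random intercept and baseline numbered 1, a covariate with assumed correlation 0.3, 0.6 or 0.8 with SGRQ gave type I error of 5.7%, 6.2% and 8.2% (2,000 trials each). A second simulation at 0.8 gave 6.7% to 7.5% when baseline was not 0. An ordinary covariate (assumed R2 0.25), imbalanced by 0.3 SD, added 0.4 points (0,1,2) to 0.7 points (1,2,3) of bias relative to the model with its main effect. Type I error was then 5.0% to 5.5%.

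**Step 4: two versions.** If success is claimed when either of two valid versions is significant, type I error is 5.4% to 6.4%, which is 0.4 to 1.4 points above 5%. Adjusting for whichever of about 16 candidates are imbalanced at p < 0.05 to 0.20 gives 5.6% to 6.3%. Free choice of any single candidate gives 7.4% to 9.4%. The last range is an upper bound, since it assumes 16 independent candidates and no rule at all.

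**The case against.** The serious harm needs baseline SGRQ in z, baseline not numbered 0, and the equation fitted exactly as printed. Inflated type I error also needs a random intercept without a random slope or robust SE. The documents establish none of the choices left open. The candidate list serves every model, including the logistic model for exacerbations, so baseline SGRQ may never have entered this one. Numbering 2, 3, 4 is the least natural reading, because the protocol counts screening apart from the three clinical visits. An analyst might also notice the failing fit: its intercept variance is estimated as zero in 66% of trials, and the unadjusted b3 would stand beside it. All of this stands, and it makes the harm conditional.

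A reader might infer more than the documents support:

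- *The primary test has 12% type I error.* Not shown. That is one combination of unstated choices.
- *b3 is biased.* Over repeated randomizations it is not, in the random-intercept, GEE and ANCOVA fits. The shift depends on the imbalance in the single trial.
- *Only baseline SGRQ matters.* Too strict: a covariate correlated about 0.8 with SGRQ also raises type I error, though the documents do not show that another candidate is that strong.
- *Numbering from 0 always makes the adjustment idle.* Shown only for the random-intercept fit. With a random slope (720 trials), adding visit*z lowered power from about 67% to about 60% and roughly doubled the shift, from about -0.11 to -0.20.
- *No primary version exists.* This is an ambiguity. The SAP introduces the displayed equation, which contains z, for the primary outcome and powers its b3, so the adjusted model reads as primary. No sentence says so outright.

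**Conclusion.** The point holds and should be fixed. As printed, the equation makes the adjusted b3 depend on an unstated label; that part is algebra. The size depends on choices that the documents do not show:

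- **Large** if baseline SGRQ is in z and baseline is numbered 1: about 12% type I error with a random intercept, power about 40% instead of about 72% for 4 points, and a shift of about -0.9 per point of imbalance. GEE and random-slope fits hold type I error but have 24% and 15% power.
- **Modest** (about 7% to 8% type I error) for another covariate correlated about 0.8 with SGRQ, if baseline is not numbered 0.
- **Small** for ordinary covariates.
- **Valid test** with baseline numbered 0 and z = baseline SGRQ, but in the random-intercept fit visit*z then removes none of the baseline imbalance.

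The open, partly imbalance-driven choice of z and the unranked pair of analyses are a secondary point, worth about 0.4 to 1.4 points of type I error for a two-version choice. The figures assume complete normal data, the SAP's SD and correlation, and the correlations with SGRQ stated above. Confidence is high for the text and the conditional figures, but not for what was actually fitted.

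**What to change.** 1. Add the main effect of every covariate: E[Y] = b0 + b1*visit + b2*treat + b3*treat*visit + c'z + a'*visit*z. A shift in numbering is then absorbed by c'z, and b3 does not change.
2. Handle baseline SGRQ by ANCOVA/MMRM on the follow-up visits, or by a constrained-baseline model, and not as both a response row and a visit*z covariate.
3. State the visit coding and the covariance structure.
4. State that one version is primary, with z fixed without regard to observed imbalance, and keep the other as sensitivity.

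The cost is SAP wording, model code and a few degrees of freedom. Much of the SAP is in the past tense; if results are already known, report the corrected model beside the model as printed and label it post hoc.

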## POWER:

### Pre-specified power calculations.

The study was powered for a single outcome. Based on a prior study, pre-intervention and baseline data from the Randomized Clinical Trial of Air Cleaners to Improve Indoor Air Quality and Chronic Obstructive Pulmonary Disease Health: Results of the CLEAN AIR Study, the trial was designed to have a sample size of 120 randomized participants (n=60 per arm), for 80% power to detect a group difference of 1.75 in change of SGRQ score, assuming a SD of 16.7 and residual SD of 6.3, based on within person correlation of 0.86 and an alpha of 0.05, (2-sided).

Table 1 summarizes the power of a two-sided test that the coefficient b3 in the model above is greater than zero at a significance level of 0.05. Power is calculated to detect shown differences in effect size for our main outcomes between groups for a sample size of 60 subjects per group. We used conservative estimates of means and standard deviations to account for uncertainty about actual observed effect sizes and variability and to minimize the chance of Type II error. We assumed a within subject correlations based on the previous study. We show adequate statistical power across a variety of assumptions. For example, we will have 90% power to detect a difference of 2.02 in total SGRQ score and a 1.49

difference in CAT score between groups. The minimal clinical important difference in SGRQ and CAT score is 4 and 2, respectively, therefore we have adequate power to detect a meaningful clinical impact. Furthermore, a similar improvement in SGRQ is seen with traditional COPD therapy, as mean between group difference in SGRQ was 2.7 favoring tiotropium, and 3.1 favoring salmeterol/fluticasone therapy compared to placebo in the UPLIFT and TORCH trials, respectively. These therapies are currently recommended as first line therapy for COPD based on GOLD Guidelines. For Specific Aim #2 we will test the difference between groups and systemic and pulmonary markers of inflammation. Similar to power analysis for Specific Aim #1, Table 1 shows we will have 80% power to detect a 1.15 ng/ml difference in serum CRP between groups. Thus, we demonstrate adequate power across several primary and secondary outcomes.

**Table 1** power for sample size of 120 (60 per group)

	Within Corr.	Residual SD	Power = 0.8	Power = 0.9
			Effect size	Effect size
Specific Aim #1				
SGRQ Total	0.86	6.3	1.75	2.02
CAT	0.77	3.7	1.30	1.49
FEV 1 (L)	0.94	0.13	0.024	0.027
Specific Aim #2				
Serum IL-8 (pg/ml)	0.55	1.47	0.72	0.83
Serum CRP (ng/ml)	0.32	1.92	1.15	1.33

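### The stated 80% power for a 1.75-point SGRQ difference does not follow from the SAP's own inputs; with 60 per arm the detectable 6-month difference is about 4.5 points, above the MCID of 4

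*SAP*

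**What the plan says.** The SAP section on pre-specified power calculations sets the sample size at 120, with 60 in each arm, and claims "80% power to detect a group difference of 1.75 in change of SGRQ score, assuming a SD of 16.7 and residual SD of 6.3". The calculation also takes a correlation of 0.86 between repeated scores on one person and a two-sided test at the 5% level.

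Table 1 lists a within-person correlation and a residual SD for each of five outcomes, with the differences detectable at 80% and 90% power for 60 per group. The text repeats some of these: "we will have 90% power to detect a difference of 2.02 in total SGRQ score and a 1.49" for CAT, and "Table 1 shows we will have 80% power to detect a 1.15 ng/ml difference in serum CRP between groups".

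The SAP describes its inputs as conservative. From MCIDs for SGRQ and CAT whose values it says "is 4 and 2, respectively, therefore we have adequate power to detect a meaningful clinical impact", it draws its conclusion on adequacy, and it later extends that conclusion to several primary and secondary outcomes. As benchmarks it cites SGRQ differences of 2.7 and 3.1 from two drug trials.

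The SAP's Analytical approach section names the treatment-by-visit coefficient b3 as the parameter of interest, with visit entered as a number. It restricts the primary analysis to randomized participants with baseline and 6-month data.

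**The concern.** An SGRQ total SD of 16.7 is large. Even with a correlation of 0.86, a difference of 1.75 points in change looks too small to detect with 60 per arm. The SAP also lists the correlation and the residual SD as separate inputs, although for SGRQ the second follows from the first and the total SD. That suggests the correlation may have been used twice.

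This calculation is the only justification given for the sample size. If 1.75 were right, the trial would have power to spare at 4 points, and a null result would be good evidence against a meaningful benefit. If the true figure is above 4, a null result would leave that question open, and readers relying on the SAP would be misled.

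**Working it through.** **Inputs** (SAP, power section and Table 1): n = 60 per arm; SGRQ total SD 16.7; residual SD 6.3; correlation ρ = 0.86; two-sided alpha 0.05. The multiplier is 1.960 + 0.842 = 2.802 for 80% power and 1.960 + 1.282 = 3.242 for 90%. Also √(2/60) = 0.1826.

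**1. What the residual SD is.** 16.7 × √(1 − 0.86) = 6.25, which matches the stated 6.3 to within rounding of the inputs. The residual SD is thus the within-person SD, with the correlation already taken out.

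**2. Reproducing the stated figures.** The formula that comes close is

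detectable difference = multiplier × residual SD × √(2(1 − ρ)) × √(2/60).

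For SGRQ at 80%: 2.802 × 6.3 × √0.28 × 0.1826 = 1.71, against the stated 1.75. For all rows:

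| Outcome | ρ | Residual SD | 80%: formula / stated | 90%: formula / stated |
|---|---|---|---|---|
| SGRQ | 0.86 | 6.3 | 1.71 / 1.75 | 1.97 / 2.02 |
| CAT | 0.77 | 3.7 | 1.28 / 1.30 | 1.485 / 1.49 |
| FEV1 (L) | 0.94 | 0.13 | 0.0230 / 0.024 | 0.0267 / 0.027 |
| IL-8 | 0.55 | 1.47 | 0.713 / 0.72 | 0.825 / 0.83 |
| CRP | 0.32 | 1.92 | 1.145 / 1.15 | 1.325 / 1.33 |

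The gaps run from about 0.3% to about 4%, which rounded inputs and a t correction can explain. Correlations range from 0.32 to 0.94, so agreement by chance is unlikely. The factor √(1 − ρ) belongs with the total SD; here it multiplies an SD that has already been reduced by it.

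**3. Correlation used once, SGRQ.**
- SD of change: 16.7 × √(2 × 0.14) = 8.84 (or 6.3 × √2 = 8.91).
- SE of the group difference: 8.84 × 0.1826 = 1.61 (1.63).
- Detectable at 80%: 2.802 × 1.61 = 4.52 (4.56). At 90%: 5.23 (5.27).
- n per arm for 1.75: 2 × (2.802 × 8.84 / 1.75)² ≈ 400 (407 with 6.3). For 4 points: 77 to 78.

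| True SGRQ difference | Power, 60 per arm |
|---|---|
| 1.75 | 19% |
| 2.02 | 24% |
| 2.7 | 38–39% |
| 3.1 | 48% |
| 4 (MCID) | 69–70% |

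**4. Other readings for SGRQ at 80% power.**

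| Reading | Detectable difference |
|---|---|
| Baseline-adjusted 6-month score (ANCOVA), SD 16.7 × √(1 − 0.86²) = 8.52 | 4.36 |
| Mean of 3- and 6-month scores minus baseline | 3.95 |
| Baseline-adjusted mean of 3 and 6 months | 3.73 |
| 6.3 taken as the SD of change | 3.22 |
| b3 per visit, visits 0, 1, 2 | 2.26–2.28 (4.52–4.56 over 6 months) |

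None of these gives 1.75.

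**5. Other outcomes.** Multiplier × residual SD × √2 × 0.1826 at 80% power, assuming that their residual SDs are defined as for SGRQ: CAT 2.68 (stated 1.30; power 55% at its MCID of 2), FEV1 0.094 L (0.024), IL-8 1.06 (0.72), CRP 1.39 (1.15).

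**6. Missing 6-month data.** The Protocol's allowance from 150 to 120 covers only those who stop smoking in the run-in; the power calculation allows for no loss after randomization. With an assumed 15% loss (51 per arm), the detectable SGRQ difference is about 4.9 and power at 4 is about 62%.

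**The case against.** The strongest objection concerns scale. The SAP says Table 1 gives power for b3, and with a numeric visit b3 is a slope per visit. On that scale power is 58% at 1.75 and 70% at 2.02, and the shortfall is 1.75 against 2.28. CAT nearly agrees (1.34 against 1.30), and the stated IL-8 and CRP figures become conservative (0.53 against 0.72, and 0.69 against 1.15). The ambiguity is real and the SAP should resolve it. It does not rescue the claim: 1.75 still fails, 2.28 per visit is about 4.5 points over 6 months, and this reading misfits the FEV1 (0.047 against 0.024), IL-8 and CRP rows. The SAP also words its target as a difference in change.

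Second, the detectable difference is not above the MCID under every estimator. Averaging both follow-up visits gives 3.7 to 3.95, with 81% to 85% power at 4. This stands as a qualification, but it is not the model the SAP writes down. Taking 6.3 as the SD of change contradicts the SD of 16.7 with a correlation of 0.86.

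Third, the double use of the correlation is inferred, and a total SD is given only for SGRQ. Both points are fair. The failure of 1.75 does not depend on the diagnosis, but the recomputed values for the other four outcomes do depend on reading their residual SDs in the same way.

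Finally, overwriting a pre-specified calculation could hide what was planned. That bears on the form of the correction, not on the need for it.

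**Conclusion.** The concern holds. On the SAP's own SGRQ inputs, 60 per arm gives 80% power for a 6-month difference in change of about 4.5 points (5.2 to 5.3 at 90%), roughly 2.6 times the stated figure (4.52 / 1.75). Power is about 19% at 1.75 and about 70% at the MCID of 4, before any loss to follow-up. The conclusion that power is adequate for a clinically meaningful effect is therefore unsupported for SGRQ. For CAT it is also unsupported on the change scale, if its residual SD is defined in the same way.

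This rests on a normal approximation, complete data, a constant within-person correlation, and either a change score or the SAP's linear b3 model taken over 6 months. A baseline-adjusted 6-month analysis narrows the figure only to about 4.4.

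The consequence is for interpretation. The 95% confidence interval would extend about 1.96 × 1.61 = 3.2 points either side of the estimate. A non-significant observed benefit larger than about 0.8 points (4 − 3.2) would thus still be compatible with a benefit of 4.

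**What to change.** - Recompute every row of Table 1 with the correlation used once, and print the formula. State whether each residual SD is the within-person SD.
- Say whether the detectable differences are 6-month changes or slopes per visit, and for which estimator. For SGRQ, report about 4.5 and 5.2 points at 80% and 90% power for the 6-month change (about 4.4 and 5.0 if baseline-adjusted).
- State power at the SGRQ MCID: about 70% with complete data, and lower under a stated assumption about missing 6-month data.
- Withdraw the statements that power is adequate for a meaningful clinical impact and across several outcomes, and the description of the inputs as conservative.
- Commit to interpreting a non-significant SGRQ result by comparing its confidence interval with 4 points.

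A dated correction placed beside the pre-specified calculation would keep the record of what was planned. The cost is SAP text and one table. The model, alpha and enrolment do not change, but the stated power becomes less favourable.
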